4.5.7 Follow-Up Assessments

Participants who complete the treatment phase of the study will return to the clinic for an end of treatment visit 4 weeks after the last dose (ET-A or ET-B). Following the completion of Study Period A, participants will be offered the opportunity to continue to receive study drug until the results of the study are known and post-trial access to crenezumab is started (via an OLE or other program) or development of crenezumab is discontinued (see Section [4.5.8](#)). For those participants that do not choose to continue study drug in Study Period B, a final safety follow-up visit will occur 16 weeks after the last dose (see [Appendix 2](#) or [Appendix 4](#)).

Any adverse event (including a clinically significant laboratory abnormality) that is unresolved at the end of the study will continue to be followed until the event is resolved or stabilized, the participant is lost to follow up, or it has been determined that the study treatment or participation is not the cause of the event. Every effort should be made to follow all serious adverse events considered to be related to study drug or study procedures until a final outcome can be reported.

Please see the study flowchart provided in [Appendix 2](#) or [Appendix 4](#) for specified follow-up assessments.

4.5.8 Study Period B Visits and Assessments

All assessments will be performed on the day of the specified visit unless a time window is specified. Assessments scheduled on the day of study drug administration should be performed prior to study drug injection or infusion, unless otherwise noted.

Study conduct and procedures during Study Period B are the same as for Study Period A (see Section [4.5.1](#)), though the frequency may be different. For SC administration, please see the study flowcharts provided in [Appendix 5](#). For IV administration, please see the study flowchart provided in [Appendix 6](#). If participants terminate participation in Study Period B, or Study Period B is terminated by the Sponsor due to discontinuation of the development of crenezumab, or participants complete Study Period B and do not enter an OLE or otherwise continue on crenezumab, participants will be asked to complete a final safety follow-up visit 16 weeks after their last dose of study drug ([Appendix 5](#) and [Appendix 6](#)).

4.5.9 Samples for Roche and Other Clinical Repositories

4.5.9.1 Overview of the Biological Sample Repositories

Blood and CSF samples will be stored at two central sample repositories, the Roche Clinical Repository (RCR) and the National Cell Repository for Alzheimer's Disease (NCRAD). The NCRAD is a national repository funded by the National Institute on Aging in the United States. The RCR and NCRAD are facilities used for the long-term storage of human biologic specimens, including body fluids, solid tissues, and derivatives thereof (e.g., DNA, RNA, proteins, peptides). The collection and analysis of repository specimens will facilitate the rational design of new pharmaceutical agents and the development of diagnostic tests, which may allow for individualized drug therapy for patients in the future. Additionally, research on the basis of these samples may lead to an enhanced understanding of AD and related disorders.

Specimens for the biological sample repositories will be collected from participants who consent to participate in this study. Repository specimens may be used to achieve the following objectives:

- To help improve the early detection of AD
- To increase knowledge and understanding of AD biology and risk factors

- To provide a resource for genome-wide association, sequencing, epigenetic, and gene expression studies related to AD or crenezumab
- To develop biomarker or diagnostic assays for AD and related disorders and establish the performance characteristics of these assays
- To study the association of biomarkers with efficacy, adverse events, or disease progression
- To study drug response, including drug effects and the processes of drug absorption and disposition

4.5.9.2 Future Research

Within 15 years after the trial is completed, the specimens in the biological sample repositories that are collected with the participants' informed consent will be made available for objectives described in Section 4.5.9.1. The implementation and use of the repository specimens is governed by a biological sample oversight committee (composed of trial leadership) in accordance with policies and procedures to ensure the appropriate use of the specimens. Sample and data sharing will be prioritized on the basis of scientific considerations and in relationship to the volume of samples available. Samples may be shared with researchers and laboratories working with Roche, Banner Alzheimer's Institute, and the University of Antioquia.

4.5.9.3 Sample Collection

The following samples will be collected for identification of dynamic (non-inherited) biomarkers to pursue the objectives described above in Section 4.5.9.1:

- Plasma and serum
- Whole blood for RNA extraction
- CSF

The following samples will be collected for identification of genetic (inherited) biomarkers to pursue the objectives described above in Section 4.5.9.1:

- Whole blood for DNA extraction

Leftover blood, serum, plasma, and CSF samples and any derivatives thereof (e.g., DNA, RNA, proteins, peptides) will be collected to pursue the objectives described above in Section 4.5.9.1.

Biological sample repository specimens will be stored for 15 years after the final study report.

The dynamic biomarker specimens will be subject to the confidentiality standards described in Section 6.10. The genetic biomarker specimens will undergo additional processes to ensure confidentiality, as described below.

4.5.9.4 Confidentiality

Given the sensitive nature of genetic data, Roche and NCRAD have implemented additional processes to ensure participant confidentiality for genetic specimens and associated data. Each specimen is "double-coded" by replacing the participant identification number with a new independent number. Data generated from the use of these specimens and all clinical data transferred from the clinical database and considered relevant are also labeled with this same independent number.

A "linking key" between the participant identification number and this new independent number is stored in a secure database system. Access to the linking key is restricted to authorized individuals and is monitored by audit trail.

Data generated from RCR and NCRAD specimens must be available for inspection upon request by representatives of national and local health authorities, and Roche monitors, representatives, and collaborators, as appropriate.

Participant medical information associated with RCR and NCRAD specimens is confidential and may only be disclosed to third parties as permitted by the Informed Consent Form (or separate authorization for use and disclosure of personal health information) signed by the participant, unless permitted or required by law.

The aggregate results of any research conducted using repository samples will be available in accordance with the effective Roche policy on study data publication except where agreed.

4.5.9.5 Participation in the RCR and NCRAD

The investigator or authorized designee will explain to each participant the objectives, methods, and potential hazards of contributing samples to the sample repositories. Participants will be told that they are free to withdraw their specimens at any time and for any reason during the storage period. A separate, specific signature will be required to document a participant's agreement to provide CSF specimens by signing the Optional CSF Substudy Informed Consent.

In the event of an RCR and NCRAD participant's death or loss of competence, the participant's specimens and data will continue to be used as part of the RCR and NCRAD research.

4.5.9.6 Withdrawal from the RCR and NCRAD

Participants have the right to withdraw their samples at any time for any reason. After withdrawal of consent, any remaining samples will be destroyed or will no longer be linked to the participant. However, if RCR samples have been tested prior to withdrawal of consent, results from those tests will remain as part of the overall research data. If a participant wishes to withdraw consent to the testing of his or her samples, the investigator must inform the Medical Monitor in writing of the participant's wishes using the Repository Subject Withdrawal Form and, if the trial is ongoing, must

enter the date of withdrawal on the Repository Research Sample Withdrawal of Informed Consent eCRF. The participant will be provided with instructions on how to withdraw consent after the trial is closed. A participant's withdrawal from Study GN28352 does not, by itself, constitute withdrawal of specimens from the repositories. Likewise, a participant's withdrawal from the repositories does not constitute withdrawal from Study GN28352.

4.5.9.7 Monitoring and Oversight

Repository samples will be tracked in a manner consistent with GCP by a quality-controlled, auditable, and appropriately validated laboratory information management system, to ensure compliance with data confidentiality as well as adherence to authorized use of specimens as specified in this protocol and in the Informed Consent Form. Study monitors and auditors will have direct access to appropriate parts of records relating to individual participation in the repositories for the purposes of verifying the data provided. The site will permit monitoring, audits, IRB/EC review, and health authority inspections by providing direct access to source data and documents related to the repository samples.

4.6 PARTICIPANT DISCONTINUATION

Participants may withdraw consent or be withdrawn from the study at any time (see criteria below). Every effort should be made to obtain information on participants who discontinue early or are withdrawn from the study (see Section 4.5.6). If a participant withdraws for reasons related to an serious adverse event, every effort will be made to follow the participant until resolution or stabilization of the event. The reason for withdrawal or early discontinuation should be recorded on the appropriate eCRF page.

Reasons for withdrawal from the study may include, but are not limited to, the following:

- Participant withdrawal of consent at any time
- Any medical condition that the investigator determines may jeopardize the participant's safety if he or she continues in the study
- Investigator determines it is in the best interest of the participant
- Participant becomes pregnant

See the Study Flowchart provided in [Appendix 1](#), [Appendix 2](#), [Appendix 3](#), [Appendix 4](#), [Appendix 5](#), and [Appendix 6](#) for assessments that are to be performed for participants who prematurely withdraw from *Study Period A* ([Appendix 1](#) to [Appendix 4](#)) or *Study Period B* ([Appendix 5](#) and [Appendix 6](#)).

Participants who discontinue from the study will not be allowed to re-enter the study.

The investigator has the right to discontinue a participant from the study for any medical condition that the investigator determines may jeopardize the participant's safety if he or

she continues in the study; for reasons of noncompliance (e.g., missed doses, visits); if the participant becomes pregnant; or if the investigator determines it is in the best interest of the participant.

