3.5.5 Additional Safety Monitoring

Laboratory tests, including hematology, chemistry, coagulation, urinalysis, and ADAs will be performed throughout the study. Electrocardiograms will be recorded regularly, including at baseline. Physical and neurological examinations will be performed throughout the study to assess adverse events, particularly any neurological events that are not consistent with normal disease progression. Suicidality assessments will be used to measure prospective suicidality (see [Appendix 7](#)). If the suicidality assessment reveals a concern about a significant level of suicidality, the participant will undergo a more detailed assessment by a qualified clinician who has experience in the evaluation of suicidal ideation and behavior, either at the site or by referral to an outside clinician.

Serum pregnancy testing will be performed at screening for all female participants of childbearing potential (see the footnotes to the study flowcharts in [Appendix 1](#), [Appendix 2](#), [Appendix 3](#), and [Appendix 4](#)). Urine pregnancy testing will be performed prior to study drug administration or PET scan for all female participants of childbearing potential. Pregnancy testing will apply to all female participants of childbearing potential unless documented (by medical records or physician's note) to be surgically sterile or postmenopausal, as defined in International Council for Harmonisation (ICH) Guidance M3 (R2), Section 11.2 (12 months with no menses without an alternative medical cause). If urine pregnancy testing returns a positive result, study drug will be held until pregnancy is verified. If pregnancy is confirmed, the participant will not receive further doses of study drug.

The incidence and nature of adverse events, serious adverse events, and laboratory abnormalities will be assessed on a regular basis by the iDMC. The committee will recommend changes to study conduct or study termination, as required.

The responsibilities and operation of the committee will be documented in the iDMC Charter.

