4.5.6 Early Termination Visit

Participants who discontinue from blinded treatment prior to completion of Study Period A (early treatment discontinuation) will be asked to stay in the study for continued safety and efficacy assessments at selected evaluation visits following completion of an ET visit (see study flowchart in [Appendix 1](#), [Appendix 2](#), [Appendix 3](#), and [Appendix 4](#)). Participants who discontinue from the study (ET), or who discontinue from blinded treatment and elect to no longer remain in the study, will be asked to return to the clinic for an ET visit (see the study flowchart in [Appendix 2](#) for participants receiving SC study drug and [Appendix 4](#) for participants receiving IV study drug). The ET visit should be 4 weeks from last dose. In addition, a final safety follow-up visit

should be completed 16 weeks after last dose to ensure adequate washout of study drug but may be scheduled sooner if needed.

Please see the study flowchart provided in [Appendix 2](#) or [Appendix 4](#) for assessments to be performed at the study completion/ET visit.

Participants that are study drug non-compliant may be withdrawn from study treatment. As standard guidance, this refers to the following: Participant misses more than 2 doses within a single, 6-month period; a one-time exception of 3 missed doses within a 6-month period will be allowed. In rare circumstances (e.g., hospitalization), the Medical Monitor has the discretion to allow additional missed doses.

In order to maximize the opportunity for all active trial participants to receive the higher dose (60 mg/kg IV) of study drug, participants who have withdrawn from study treatment *in Study Period A*, but remain in the study for safety and efficacy assessments will be permitted a one-time opportunity to return to the study and to receive the higher IV dose, provided they did not discontinue treatment due to an adverse event related to study drug, the investigator judges it is safe to restart study drug, and the participant consents to receive IV administration of study drug going forward. If the participant has not completed a complex visit within 6 months of restarting study drug, a complex visit should be completed prior to reinitiating study drug. The investigator may also order unscheduled laboratory assessments as necessary to ensure safety and appropriateness to resume study drug.

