5.3.2 Estimands

Primary endpoint estimands are defined on the basis of the following attributes.

- Population: *PSEN1* E280A mutation carriers as defined by the inclusion/exclusion criteria specified in the protocol (mITT)
- Treatments: crenezumab versus placebo either by SC administration or by IV administration

- Variables: 1) annualized rate of change in the API ADAD Composite Cognitive Test total score and 2) annualized rate of change in the FCSRT Cueing Index
- Intercurrent events:
 - Events that lead to treatment withdrawal due to an adverse event. A treatment strategy will be applied where all observed values will be used regardless of the occurrence of the intercurrent event.
 - Death not due to AD. A hypothetical strategy will be applied where all values will be censored after the occurrence of the intercurrent event.
 - Death due to AD. All values on the primary endpoint after this event will be imputed as 0, the worst score possible
 - Pregnancy that leads to treatment withdrawal. A treatment strategy will be applied where all observed values will be used regardless of the occurrence of the intercurrent event.
 - Resumption of dosing after treatment discontinuation post-protocol amendment, version 8. A treatment policy strategy will be applied where all observed values will be used regardless of the occurrence of the intercurrent event.
 - Dose change from SC to IV administration. A treatment policy strategy will be applied where all observed values will be used regardless of the occurrence of the intercurrent event.
 - Events that lead to treatment interruption or withdrawal due to coronavirus disease 2019 (COVID-19) diagnosis. A hypothetical strategy will be applied where all primary efficacy data will be censored between COVID-19 diagnosis and recovery (if recovery date is missing, then all primary efficacy data after COVID-19 diagnosis date will be censored).
 - *Concurrent use of protocol-defined prohibited medications that can potentially impact cognition (e.g., anti-psychotics, anticonvulsants, benzodiazepines, etc.). A treatment policy strategy will be applied where all observed values will be used regardless of the occurrence of the intercurrent event.*
- Population-level summary: difference in annualized rate of change between the mutation carrier crenezumab arm and mutation carrier placebo arm

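### Protocol 4.6 allows follow-up to end for pregnancy or missed doses, while other sections stop only study drug and the SAP plans to use the later data

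*Protocol*

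**What the plan says.** **Leaving the study.** Protocol 4.6 includes "Participant becomes pregnant" in its list of possible reasons for withdrawal from the study. Its closing paragraph gives the investigator the right to discontinue a participant from the study "for reasons of noncompliance (e.g., missed doses, visits); if the participant becomes pregnant". It adds: "Participants who discontinue from the study will not be allowed to re-enter the study". One sentence softens this, with a pointer to Section 4.5.6: "Every effort should be made to obtain information on participants who discontinue early or are withdrawn from the study".

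**Stopping study drug.** Protocol 3.5.5 says of pregnancy: "If pregnancy is confirmed, the participant will not receive further doses of study drug". Protocol 4.5.6 says of missed doses: "Participants that are study drug non-compliant may be withdrawn from study treatment". It gives a guide threshold of more than 2 missed doses in 6 months, with a one-time allowance of 3. The same section says that participants who stop blinded treatment in Period A "will be asked to stay in the study for continued safety and efficacy assessments at selected evaluation visits". Footnote a of Appendices 2 and 4 names the complex visits at which their cognitive assessments continue.

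**Analysis.** SAP 5.3.2 lists as an intercurrent event: "Pregnancy that leads to treatment withdrawal. A treatment strategy will be applied where all observed values will be used". SAP 5.3.3 fits a random coefficient regression model to all observations under a missing-at-random assumption.

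**The concern.** One event can be handled in two ways, both compliant with the protocol, with opposite consequences for the data. Under 3.5.5 and 4.5.6 the participant stops drug and goes on supplying scores on both primary endpoints. Under 4.6 she or he leaves and cannot return.

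For pregnancy, the SAP's chosen strategy works only if values after the event exist. If the participant has left the study, they do not, and the model extrapolates from earlier visits. Investigators can also differ in how they use the discretion, so identical events may give different patterns of missing data. Missing data of this kind are avoidable, because the visits are already in the schedule.

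**Working it through.** This is mainly a comparison of texts; the arithmetic is background.

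**1. Consequence of each event, by section**

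| Event | Protocol 4.6 | Elsewhere in the protocol | SAP |
|---|---|---|---|
| Pregnancy | May leave the study; no re-entry | No further study drug (3.5.5); treatment discontinuers in Period A asked to stay (4.5.6, Appendices 2 and 4) | Treatment withdrawal; all observed values used (5.3.2) |
| Missed doses | May be discontinued from the study; no threshold; no re-entry | May be withdrawn from treatment, with a threshold (4.5.6); asked to stay | Not a listed intercurrent event; the data enter because the model uses all observations (5.3.3) |

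**2. What a study leaver still supplies.** The retention sentence in 4.6 points to 4.5.6. For someone leaving the study, 4.5.6 provides an early termination visit 4 weeks after the last dose and a safety visit at 16 weeks. Version A of the termination visit includes the cognitive batteries. No cognitive visits follow. The SAP's amendment rationale itself notes that no later data are expected after study discontinuation.

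**3. A linked effect.** The one-time return to dosing at the IV dose (4.5.6) is open only to participants who stayed in the study. SAP 5.3.2 handles resumed dosing by treatment policy. Withdrawal under 4.6 closes that route.

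**4. What is lost per person (illustration).** The FCSRT is scheduled after baseline at Weeks 24, 52, 76, 104, 128, 156, 180, 208, 232 and 260, which is 10 visits. A carrier who leaves after Week 104 misses the last 6, plus any visits beyond Week 260 before the common close.

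**5. Power background.** Inputs from Protocol 4.10.8: 100 per arm, 25% dropout, CV 65%, 30% reduction, two-sided 0.05. In units of the placebo mean decline, the difference is 0.30 and the SD 0.65; evaluable n = 100 × 0.75 = 75 per arm.

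Power = Φ(0.30 / (0.65 × √(2/75)) − 1.96) = Φ(2.826 − 1.960) = Φ(0.866) = 80.7% (80.2% with the noncentral t). The plan's figure of at least 80% is reproduced.

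Now assume 5 or 10 points of extra study withdrawal in each arm. This is an assumption; the documents give no count. The 84 per arm comes from the simulation in SAP Appendix 2, and 0.04 is the alpha now given to the API composite.

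| Per arm, alpha | 25% dropout | 30% | 35% |
|---|---|---|---|
| 100, 0.05 | 80.7% | 78.0% | 74.9% |
| 84, 0.05 | 73.6% | 70.6% | 67.4% |
| 84, 0.04 | 70.4% | 67.3% | 64.0% |

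Each extra 5 points costs about 3 points of power. This overstates the cost for the planned model, which keeps the observations made before withdrawal and uses data after Week 260.

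**The case against.** The best defence is that the protocol already sets the right default. Section 4.6 only says what reasons may include and what the investigator has the right to do. Sections 4.3.1.3, 4.4.1.3 and 4.5.6 and the flowcharts repeatedly invite participants off drug to stay, and missed doses have their own rule that ends in treatment withdrawal. The SAP also plans sensitivity analyses. The design already allowed for 25% dropout, and with recruitment finished a late edit protects less Period A follow-up.

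Much of this stands, and it rules out several stronger readings:

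- A reader might infer that pregnancy or missed doses must end study participation. The text permits this and does not require it.
- A reader might infer that the estimand explicitly needs the data after both events. It names pregnancy only. The case for missed doses rests on the model using all observations and on the handling of resumed dosing.
- A reader might take the fall in one participant's time spread (sum of squares of visit times, from 27.5 to 2.5 years squared if follow-up stops at Week 104) as an 11-fold loss of information. That ratio applies to an individual least-squares slope. With a random slope, the loss ratio is (1 + r/2.5) / (1 + r/27.5), where r is residual variance over slope variance. For assumed r of 2.5, 10 and 27.5 years squared it is about 1.8, 3.7 and 6.
- A reader might infer that this dropout is informative because missed doses signal cognitive decline. That is plausible, but neither document says so.

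The defence does not remove the conflict. The retention sentence in 4.6 leads to a termination visit and a safety visit, not to continued cognitive follow-up. The sensitivity analyses probe the gap only in part. The hypothetical-strategy analysis censors after pregnancy-related treatment withdrawal, so for someone who has already left it uses essentially the same data as the primary analysis. The immediate-loss-of-effect model needs observations after drug is stopped. Control-based mean imputation identifies completers by a score at ET-A or ET-B, and a study leaver is asked to attend one of those visits, so it is unclear whether that person would count as missing.

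**Conclusion.** The inconsistency is real and bears on the primary estimand. Protocol 4.6 allows study withdrawal without re-entry for two events that the other sections attach to stopping study drug. Where a site uses the option, values that the SAP's pregnancy strategy or the primary model would use are not collected, and missing at random has to stand in for them.

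The size is unknown. Neither document says how many participants left for these reasons, and the power figures above rest on assumed extra dropout and a simpler test. This is a worthwhile, low-cost correction; nothing here shows that the primary result is compromised. The conclusion assumes that sites may read 4.6 as it is written, and it applies most directly to Period A, where the request to stay after stopping drug is stated. No view is taken on when study drug should be stopped.

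**What to change.** Reconcile Protocol 4.6 with 3.5.5, 4.5.6 and SAP 5.3.2:

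- State in 4.6 that pregnancy and missed doses are not in themselves grounds for ending study follow-up. Keep the existing consent, safety and best-interest grounds.
- State that participants off study drug for these reasons are asked to continue the complex-visit cognitive, CDR and MCI/AD assessments already scheduled in Appendices 2 and 4.
- In SAP 5.3.2, say how treatment withdrawal for missed doses is handled.
- Say whether the retention rule also applies in Period B, since 4.6 covers both periods and 4.5.6 gives Period B leavers only a safety visit.

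Imaging and lumbar puncture in pregnancy stay under the existing protocol rules. The cost is a wording change, a line in the SAP and some extra site effort to retain these participants; no new visits are needed for Period A.
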